8. STATISTICAL METHODS

All data collected during this study will be presented in subject data listings. All statistical analyses will be performed using SAS® for Windows, version 9.4 or later.

8.1 Summarizing and Tabulating the Collected Data

All data collected will be summarized according to the variable type:

- Continuous data summaries will include number of observations, mean, standard deviation, median, and minimum and maximum values.
- Categorical data summaries will include frequency counts and percentages.

8.1.1 Subject Disposition and Withdrawals

The disposition of all subjects who sign an ICF will be provided. The number of subjects screened, rescreened, screen failure, received treatment, completed, and discontinued during the study, as well as the reasons for all post treatment discontinuations will be summarized. Disposition and reason for study discontinuation will also be provided as a by-subject listing.

In addition, there will also be a listing of all discontinued subjects, which will provide the clinical trial center and the specific reason for discontinuation.

8.1.2 Protocol Deviations

The deviations occurring during the clinical trial will be summarized descriptively. Additionally a by-subject listing of all deviations will also be prepared.

8.1.3 Demographics and Baseline Characteristics

Demographics and baseline characteristics (i.e., Age, Gender, Time since HIV diagnosis, Viral load at Screening Visit, etc.) will be summarized using appropriate descriptive statistics.

Medical history of the subjects will also be summarized and also provided as a by-subject listing.

8.1.4 Prior and Concomitant Medications

Prior and concomitant medications will be summarized for the Safety population. All prior and concomitant medications recorded in the eCRFs will be coded to generic term and all matching Anatomic Therapeutic Classification (ATC) codes using WHO Drug Summaries will be prepared using the coded terms. All prior and concomitant medications recorded in the eCRFs will also be listed.

8.1.5 Anti-Retroviral Therapy (ART)

Anti-retroviral therapy and re-initiation of anti-retroviral therapy data will be summarized for the Safety Population. All such medications recorded in the eCRFs will be coded to generic term and all matching Anatomic Therapeutic Classification (ATC) codes using WHO Drug. Summaries will be prepared using the coded terms. All anti-retroviral therapy recorded in the eCRFs will also be listed.

In addition, Virologic failure subjects will have a long term safety follow up visit at 6 months and 1 year after the virologic failure visit. Any changes in ART regimen during this time will be captured and presented as a by-subject listing.

8.1.6 Treatment Exposure

All data from administration of study drug will be presented. In addition the following summaries will be included:

- Duration of PRO 140 treatment (in weeks)
 - At the Assigned dose
 - At the Rescue Dose (if applicable)
 - Combined Assigned and Rescue dose.
- Proportion of participants completing 24, 48 weeks of PRO 140 treatment.
 - At the Assigned dose
 - Combined Assigned and Rescue dose
- Duration of PRO 140 treatment (in weeks) at the time of virologic failure

8.2 Analysis of Study Outcome Measures

8.2.1 Safety Outcome Measures

The Safety population will be used for the analysis of safety assessments.

8.2.1.1 Adverse Events

Adverse events will be coded using Medical Dictionary for Regulatory Activities (MedDRA). TEAEs are defined as events with an onset on or after the first treatment. TEAEs will be summarized by treatment group, System Organ Class (SOC), and preferred term (PT). The following TEAE summaries will be provided:

- Overall (*i.e.*, regardless of severity or relationship to treatment)
- By severity grade (mild, moderate, severe, life threatening or death for SAEs)
- By relationship to study treatment (definitely related, probably related, possibly related, remotely related or unrelated)

In addition, separate summaries of SAEs, and AEs resulting in discontinuation of study treatment will be presented.

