2. PROTOCOL DESIGN AND OBJECTIVES

2.1 Study Objectives

The objective of this study is to assess the clinical safety and treatment strategy of using PRO 140 SC 350mg or 525mg or 700mg as long-acting, single-agent maintenance therapy for the chronic suppression of CCR5-tropic HIV-1 infection. In addition, the prognostic factors of therapeutic success of PRO 140 monotherapy will be evaluated.

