2.2 Design Overview

This study is a Phase 2b/3, multi-center, randomized, two-part, open-labeled study designed to evaluate safety and tolerability of the strategy of shifting clinically stable patients receiving suppressive combination antiretroviral therapy to PRO 140 monotherapy and maintaining viral suppression for 48 weeks following study entry.

Consenting patients will be shifted from combination antiretroviral regimen to weekly PRO 140 monotherapy for 48 weeks during the Treatment Phase with the one week overlap of existing retroviral regimen and PRO 140 at the beginning of the study treatment and also one week overlap at the end of the treatment in subjects who do not experience virologic failure. The first ~150 eligible subjects were enrolled to receive PRO 140 350mg SC weekly injection in a single-arm study. Subsequently, next ~150 subjects were randomized 1:1 to PRO 140 350mg (Group A) or PRO 140 525mg (Group B). An additional ~200 subjects will be randomized 1:1 to PRO 140 525mg (Group B) or PRO 140 700mg (Group C).

➤ **For the first ~150 enrolled subjects:**

- **Part 1:** 48-week, single-arm, open-label treatment phase
 - PRO 140 350mg SC weekly injection (Group A)

➤ **For the subsequent ~150 enrolled subjects:**

- **Part 1:** 48-week, randomized, two-arm, open-label treatment phase
 - PRO 140 350mg SC weekly injection (Group A)
 - PRO 140 525mg SC weekly injection (Group B)

➤ **For the subsequent ~200 enrolled subjects:**

- **Part 1:** 48-week, randomized, two-arm, open-label treatment phase
 - PRO 140 525mg SC weekly injection (Group B)
 - PRO 140 700mg SC weekly injection (Group C)

As noted below, subjects in Group A or Group B that experience virologic failure prior to week 48 in Part 1 have option of entering Part 2 wherein they receive higher dose of PRO 140 for remainder

of treatment phase or may re-initiate prior ART regimen (or an alternative regimen selected by their treating physician) at the discretion of the subject and Investigator.

Part 2 – Rescue Arm for Group A and Group B subjects

- **Part 2 for Group A:** single arm, open-label treatment phase for Group A subjects electing to receive PRO 140 525mg SC after experiencing virologic failure on 350mg SC/weekly dose
- **Part 2 for Group B:** single arm, open-label treatment phase for Group B subjects electing to receive PRO 140 700mg SC after experiencing virologic failure on 525mg SC/weekly dose

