3. STUDY OUTCOME MEASURES

3.1 Primary Outcome Measures

The following outcome measures will be assessed for all subjects and within each treatment group for PRO 140 350mg, 525mg and 700mg dose.

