8.2.1.2 Injection Site Reaction assessment

All data from the injection site reaction assessments of the repeated subcutaneous administration of PRO 140 will be descriptively summarized.

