8.2.1.3 Pain Assessment using Visual Analog Scale (VAS)

All data from the VAS assessment of the repeated subcutaneous administration of PRO 140 will be summarized descriptively by treatment group.

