The percentages of subjects with completing 24 and 48 weeks of PRO 140 treatment with HIV-1 RNA <50 copies/mL will be presented descriptively by treatment groups for the ITT and PP populations:

- At the Assigned dose
- Combined Assigned and Rescue dose

8.2.2.9 Mean change in CD4 cell count, at each visit within the Treatment Phase

The raw and change from baseline in CD4 cell count will be summarized for each week during the treatment phase. For change from baseline summaries, subjects with an undefined change from baseline, because of missing data, will be excluded.

8.2.2.10 To evaluate the prognostic factors of therapeutic success of PRO 140 monotherapy during the Treatment Phase

- CCR5 Receptor Occupancy: To confirm occupancy of CCR5 receptors on T-cells and monocytes or both while subjects are on PRO 140 Monotherapy and to monitor changes in CCR5 receptor occupancy status associated with changes in HIV-1 RNA levels and CD4 counts.

Data for CCR5 Receptor Occupancy will be provided from the external vendor InCell Dx. All data will be presented as a by-subject listing.

- CCR5 Genotyping Status (heterozygotes or homozygotes)

Data for CCR5 Genotyping Assay will be provided from the external vendor InCell Dx. All data will be presented as a by-subject listing.

- gp120 genotyping: To identify potential polymorphisms that may decrease PRO 140 susceptibility and may affect response to PRO 140

Data for gp120 genotype will be provided by external vendor Monogram Biosciences. All data from Monogram Biosciences will be presented as a by-subject listing.

- Baseline HIV-1 RNA Single Copy levels: To monitor changes in HIV-1 RNA single copy levels while subjects are on PRO 140 Monotherapy.

Data for HIV-1 RNA single copy assay will be provided by external vendor bioMontor Lab. All data from will be presented as a by-subject listing.

- **Immune Activation Markers:** To monitor changes in CRP, IL-6, and D-Dimer levels while subjects are on PRO 140 Monotherapy.
Data for immune activation markers will be provided by external vendor Covance. All data will be presented as by-subject listings.
- **PhenoSense® Entry Assay:** Baseline IC50, IC90 and maximal inhibition for PRO 140 and change from baseline while subjects are on PRO 140 Monotherapy
Data for PhenoSense Entry assay will be provided by external vendor Monogram Biosciences. All data will be presented as by-subject listings.

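### By-dose safety tables pool rescue-dose and post-PRO 140 events with events on the assigned dose; tables split by period at onset should be added

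*SAP*

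**What the plan says.** SAP 8.2.1.1 sets the rule for adverse events: "TEAEs are defined as events with an onset on or after the first treatment. TEAEs will be summarized by treatment group". It adds summaries by severity and by relationship, and separate summaries of SAEs and of AEs leading to discontinuation. Protocol 8.7.5.1 uses essentially the same wording.

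For pain, SAP 8.2.1.3 says: "All data from the VAS assessment of the repeated subcutaneous administration of PRO 140 will be summarized descriptively by treatment group". For injection-site reactions (ISRs), SAP 8.2.1.2 names no grouping: "All data from the injection site reaction assessments of the repeated subcutaneous administration of PRO 140 will be descriptively summarized". However, SAP 3.1 requires all primary outcomes, safety included, to be assessed overall and "within each treatment group for PRO 140 350mg, 525mg and 700mg dose".

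SAP 2.4.1 defines Groups A, B and C as 350, 525 and 700 mg. SAP 2.2 describes Part 2, a rescue arm with "Group A subjects electing to receive PRO 140 525mg SC after experiencing virologic failure" on 350 mg, and a matching step from 525 to 700 mg for Group B.

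Elsewhere the SAP does separate doses. Section 8.1.6 gives treatment duration at the assigned dose, at the rescue dose and for both together. Section 8.2.2.8 gives suppression at the assigned dose and under the label "Combined Assigned and Rescue dose".

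**The concern.** The stated objective is to "assess the clinical safety and treatment strategy of using PRO 140 SC 350mg or 525mg or 700mg". A reader will take a column headed 350 mg as the safety experience on 350 mg. Under the plan that column also holds events that began on 525 mg. It further holds events in failures who have stopped PRO 140 and are back on ART. The 525 mg column likewise takes in events on 700 mg. Group C has no rescue dose, but its failures still contribute post-drug events.

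If tolerability depends on dose, the columns would not describe the doses they name. An AE that ended treatment on 700 mg rescue would appear in the discontinuation summary under 525 mg. Because every analysis is descriptive, these tables are the trial's whole safety result.

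**Working it through.** The plan gives no figure to reproduce here: the sample size rests on clinical judgment and no test is planned. The check has three parts.

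**1. Where each event lands under SAP 8.2.1.1**

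| Event | Treatment at onset | Column |
|---|---|---|
| Group A, before failure | 350 mg | 350 mg |
| Group A, rescue | 525 mg | 350 mg |
| Group B, rescue | 700 mg | 525 mg |
| Failure in any group, after last PRO 140 dose | ART | starting dose |

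No safety section of SAP 8.2.1 separates these rows. The Safety population (SAP 6.3) requires only one dose, and the planned-table list (SAP 9.2) adds no split.

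**2. Share of PRO 140 person-weeks at the rescue dose (illustration)**

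Inputs: a 48-week Treatment Phase (documents). Assumptions: failure fraction f = 0.20 to 0.50, uptake among failures u = 0.5 to 1.0, week of failure w = 12 to 20, rescue weeks r, and no other dropout.

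Share = f·u·r / [(1−f)·48 + f·w + f·u·r]

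With rescue continuing to week 48 (r = 48 − w):
- Low: f = 0.20, u = 0.5, w = 20, r = 28 gives 2.8 / (38.4 + 4 + 2.8) = 2.8/45.2 = 6.2%.
- High: f = 0.50, u = 1.0, w = 12, r = 36 gives 18 / (24 + 6 + 18) = 18/48 = 37.5%.

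With rescue lasting only 12 weeks (r = 12):
- Low: 1.2 / (38.4 + 4 + 1.2) = 1.2/43.6 = 2.8%.
- High: 6 / (24 + 6 + 6) = 6/36 = 16.7%.

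**3. All-AE collection after the last dose**

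- Non-failures: the last visit is 4 weeks after T48 (Protocol Table 4-3a), so about 4 weeks.
- Failures: visits run every 4 weeks until re-suppression, for at most 6 months after ART restarts (Table 4-3b), and all AEs are collected until re-suppression (Protocol 9.1.1). Taking the last dose and the ART restart as both at the VF visit, this is about 4 weeks (VF-FU1) up to a ceiling of about 26.
- Difference: 0 to 26 − 4 = 22 weeks.

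At the 6- and 12-month long-term visits, only SAEs and AEs judged at least possibly related are captured.

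**The case against.** **Attribution is not undefined.** A reader might infer that the SAP leaves open which group an event belongs to. It does not. The open-ended TEAE definition, the list of Groups A to C and the description of Part 2 as a rescue arm for Group A and B subjects together point to the starting group. That reading suits a treatment-strategy objective, and those tables should stay. What stands is that they cannot also serve as safety by dose.

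**Mitigants exist.** Relationship tables, by-subject listings and the 8.1.6 durations all help. Protocol 9.1.2 also has a not-applicable category for treatment impact once a subject has left the treatment phase. None of these gives event counts by dose at onset.

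**Dose-related tolerability is not established.** It is tempting to read Protocol 6.2 as expecting more discomfort at the higher doses. It says only that patients with low body fat may find the 1.5 mL or 2 mL injections uncomfortable. Protocol 6.2 and 6.4 also allow other volumes per injection, so dose does not fix volume. Studies 1101 (single IV doses) and 2101 (SC doses up to 324 mg over three weeks) saw no dose-related pattern. They do not settle 700 mg weekly over months.

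**The illustration cannot be turned into head counts.** Part 2 is offered to ongoing subjects, so Group A subjects who failed and left before it was available could not enter. Uptake of 50-100% may be too high for that group. The 26 weeks is likewise a ceiling: in the earlier 350 mg monotherapy study and its extension, failures with available data all re-suppressed on ART (Protocol 1.4.2.7).

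**No cut-off is supported by the documents.** A customary 28-day window would still count early ART-period events as on PRO 140. Protocol 1.4.2.5 reports high receptor occupancy for 29 days after single IV doses. The length of the window needs the sponsor's own justification.

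**Conclusion.** The point holds as a gap in presentation, and the SAP should be changed. Followed as written, the plan pools three kinds of event under the starting dose, although it already separates assigned from rescue dose for exposure and assigned from combined dose for suppression.

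The size cannot be known from the documents. Under the stated assumptions, with rescue to week 48, about 6-38% of a group's PRO 140 person-weeks in Groups A and B would be at the rescue dose. The share is lower if rescue is shorter or if earlier Group A failures could not enter Part 2. Post-drug collection of all AEs is about 4 weeks in non-failures and at most about 26 weeks in failures who do not re-suppress.

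A reader might infer that a dose comparison or an error rate is biased. The documents do not support that: SAP 7.4 plans no inferential statistics. The effect is on how the descriptive by-dose tables read.

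**What to change.** Keep the by-starting-group tables and add the following to SAP 8.2.1:

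1. Descriptive TEAE, SAE and AE-discontinuation tables within starting group, split by period at onset: assigned dose, rescue dose, after the last PRO 140 dose. Show the 8.1.6 durations beside them.
2. A pre-specified end to the on-treatment window, measured from the last PRO 140 dose, with the sponsor justifying its length. The VF visit is not a safe anchor, because Protocol 4.2 lets PRO 140 continue while a new ART regimen is arranged. Flag events that start after ART is resumed.
3. VAS pain split by the dose of the preceding injection, since it is scored before dosing for the period since the last treatment. Split ISRs by dose where the data link a reaction to an injection, and otherwise by dose period at assessment. Protocol 7.12 covers current and previous sites, and the documents do not show that such a link is recorded. Note that neither measure applies to doses self-administered at home.
4. A statement that rescue columns hold only virologic failures, later in time, and are not a randomised comparison.

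The cost is SAP wording and programming. AE collection does not change, and the ISR fallback avoids needing new data. The downside is more tables, and a subject can appear in more than one column.

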8.2.1.2 Injection Site Reaction assessment

All data from the injection site reaction assessments of the repeated subcutaneous administration of PRO 140 will be descriptively summarized.

8.2.1.3 Pain Assessment using Visual Analog Scale (VAS)

All data from the VAS assessment of the repeated subcutaneous administration of PRO 140 will be summarized descriptively by treatment group.

8.2.1.4 Clinical Laboratory Evaluations

All available results of the clinical laboratory evaluations will be listed and summarized. Laboratory evaluations include hematology, biochemistry, serology and urinalysis.

8.2.1.4.1 Laboratory Values over Time

Summary statistics of raw data and change from baseline values for each laboratory parameter will be presented. Data will be summarized as appropriate to the variable type.

For change from baseline summaries, subjects with an undefined change from baseline, because of missing data, will be excluded.

8.2.1.4.2 Individual Subject Changes (Shift Tables)

Individual subject changes will be identified through shift tables. Shift tables will be presented for each laboratory parameter with counts and percentages of subjects, for shift (change) from baseline.

8.2.1.1 Clinically Significant Abnormalities

A by-subject listing of treatment-emergent clinically significant laboratory values, by treatment group, will be prepared.

8.2.1.2 Vital Signs

Tabulations of raw data and change from baseline values will be presented by visit for each vital sign parameter [*i.e.*, systolic BP (mmHg), diastolic BP (mmHg), temperature ($^{\circ}$ C), heart rate (bpm), respiratory rate (rpm)].

8.2.1.3 Electrocardiogram (ECGs)

The ECG parameters include: ventricular rate (beats per minute), PR interval (msec), QRS interval

(msec), QT interval (msec), and QTcF interval (msec).

8.2.1.3.1 ECG Values over Time

Descriptive statistics of raw data and change from baseline values for each ECG measurement will be presented. For change from baseline summaries, subjects with an undefined change from baseline, because of missing baseline data, will be excluded.

8.2.1.3.2 Individual Subject Changes (Shift Tables)

Individual subject changes will be identified through shift tables. Shift tables will be presented for the investigator ECG interpretation (i.e., Normal, Abnormal (not clinically significant) and Abnormal (clinically significant)) with counts and percentages of subjects, for shift (change) from baseline.

8.2.1.4 Physical Examination

All physical examination findings will be listed and any abnormality will be summarized.

8.2.2 Efficacy Outcome Measures

The primary analysis of efficacy outcome measures will be conducted on the ITT population. The Per Protocol (PP) population will be used as a supportive analysis.

8.2.2.1 Proportion of participants experiencing virologic failure at the assigned dose

The percentages of subjects with virologic failure (as defined in [Section 7.5.6](#)) will be presented descriptively by treatment groups for the ITT and PP populations.

Note: Assigned dose refers to the dose allocated at the time of randomization/enrollment.

8.2.2.2 Time to virologic failure at the assigned dose

The number of observations, mean, standard deviation, median, and minimum and maximum values will be presented to summarize time to virologic failure (as defined in [Section 7.5.7](#)) by treatment groups for the ITT and PP populations.

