#### 7.10.9 Plasma HIV-1 RNA level and TruCount T Assay

- Frequency of testing: At SV, T1, T2, T4, T6, T8, T10, T12, T14, T16 and T17, at least once every four weeks between T18-21, T22-25, T26-29, T30-33, T34-37, T38-41, T42-45, T48 and at VF visits when subject comes to clinic. In addition, blood sample will also be collected at all Virologic Failure Follow-up (VF-FU) Visits or Non-Virologic Failure Follow-up (NVF-FU) Visits.
- To assess antiretroviral therapeutic response to PRO 140 or cART regimen

**Note:** Plasma HIV-1 RNA level will be measured using Human Immunodeficiency Virus 1 (HIV-1), Quantitative, RNA (Taqman® Real-Time PCR) test.

TruCount T Assay includes measurement of Absolute Lymphocytes, CD3 cell count, CD4 cell count, CD8 cell count, CD3%, CD4% and CD8%

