#### **8.7.4 Efficacy Analysis**

All data from the primary and secondary outcome measures will be summarized and tabulated according to the variable type:

- Time to event data will be depicted using Kaplan-Meier plots
- Continuous data summaries will include number of observations, mean, standard deviation, median, and minimum and maximum values.
- Categorical data summaries will include frequency counts and percentages.

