7.5.5 Time to Virologic Failure

The date of virologic failure is defined as the date of the second assessment of the two (2) consecutive plasma HIV-1 RNA levels of ≥ 200 copies/mL when virologic failure is confirmed.

For the censored subjects (i.e., subjects who do not have an event) the date of event will be:

- The time of the last visit data; if the subject completes the trial;

- The time of the early termination for those subjects who withdraw or early terminate from the trial.

[for those with virologic failure]

Time to virologic failure = (Date of first HIV-1 RNA levels of ≥ 200 copies/mL – Date of first treatment) +1

[for those without virologic failure]

Time to virologic failure = (Date of last visit/ early termination – Date of first treatment) +1

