7.5.7 Time to Viral re-suppression

This will be assessed for all subjects experiencing virologic failure. The date of viral re-suppression is defined as the date of first assessment where plasma HIV-1 RNA levels of <50 copies/mL after virologic failure.

Time to viral re-suppression = (Date of first HIV-1 RNA levels of < 50 copies/mL – Date of virologic failure) +1

7.5.8 Time to Viral re-suppression after re-initiation of oral combination antiretroviral regimen (Re-ART)

This will be assessed for all subjects experiencing virologic failure and oral combination antiviral therapy is re-initiated. The date of viral re-suppression is defined as the date of first assessment where plasma HIV-1 RNA levels of <50 copies/mL after virologic failure.

Time to viral re-suppression after Re-ART = (Date of first HIV-1 RNA levels of < 50 copies/mL – Date of first re-initiation of oral combination regimen) +1

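### SAP 7.5.5 gives two dates for virologic failure, and SAP 8.2.2.2 summarises the censored time by mean and SD in place of the protocol's Kaplan-Meier display

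*SAP*

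**What the plan says.** **Event date.** The text of SAP 7.5.5 reads: "The date of virologic failure is defined as the date of the second assessment of the two (2) consecutive plasma HIV-1 RNA levels". The formula in the same section, for subjects with VF, subtracts the first treatment date from "Date of first HIV-1 RNA levels of ≥ 200 copies/mL". SAP 7.5.7 then measures re-suppression time as the first value below 50 minus the VF date: "copies/mL – Date of virologic failure) +1".

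**Censoring.** SAP 7.5.5 names subjects without an event as censored. Completers get "The time of the last visit data; if the subject completes the trial", and subjects who leave get their early termination date.

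**Summary.** SAP 8.2.2.2 says "The number of observations, mean, standard deviation, median, and minimum and maximum values will be presented to summarize time to virologic failure", by treatment group, for the ITT and PP populations. No method for censored data is named, here or elsewhere in the SAP, and SAP section 9 plans only listings and summary tables. Protocol 8.7.4 says: "Time to event data will be depicted using Kaplan-Meier plots". SAP 8.1.6 separately reports "Duration of PRO 140 treatment (in weeks) at the time of virologic failure".

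**Schedule.** Protocol 7.10.9 sets the HIV-1 RNA tests: "At SV, T1, T2, T4, T6, T8, T10, T12, T14, T16 and T17, at least once every four weeks between T18-21", then once in each four-visit block up to T42-45, then T48. Protocol 4.2.3 restarts ART at week 47 in suppressed subjects. The last follow-up visit without VF is 4 weeks after T48 (protocol Table 4-3).

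**The concern.** The proportion with VF and the time to VF head the list of primary efficacy measures (SAP 3.1.2). No inferential statistics are planned (SAP 7.3 and 7.4), so these descriptive figures are the result.

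Two rules for the event date give two answers from the same data. If the formula ends time to VF at the first value and 7.5.7 starts re-suppression at the second, the interval between the values belongs to neither measure.

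A plain mean over all subjects treats a non-failing subject's follow-up time as if VF had occurred at its end. The result then depends on how long the trial follows people. The censoring date for completers also falls after ART has restarted, although the measure is meant to describe the assigned dose.

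**Working it through.** The documents state no VF rate, dropout rate or expected time to VF, so there is no plan figure to reproduce. The rates below are assumptions.

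**1. Day counts from the schedule.** With T1 as day 1, visit Tk falls on day 1 + 7(k − 1).
- T47 = day 323; T48 = day 330; last follow-up visit = 330 + 28 = day 358.
- A completer without VF is therefore censored 358 − 323 = 35 days after ART restart if restart is at T47, or 358 − 330 = 28 days if week 47 is read as day 330 (visit windows aside).

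**2. Gap between the two VF dates.** Simulation of 1,000,000 subjects, in weeks since first dose (Tn = week n − 1). Tests are at T2, T4, ..., T16, T17, one random visit in each block T18-21 to T42-45, and T48. Rebound is exponential from week 1 with cumulative risk p by week 46. Every value after rebound is at least 200. There is no dropout, there are no extra draws, and non-failures have their last visit at week 51.
- At p = 40%, about 37.6% have confirmed VF. The gap averages 3.0 weeks (median 2, range 1 to 7): about 1.9 weeks if the first value is at T2 to T16, and about 3.7 weeks if later. The 7-week maximum is a test at T18 followed by one at T25.

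| Assumed rebound risk | VF by week 24, first value | VF by week 24, second value |
|---|---|---|
| 20% | 10.1% | 8.3% |
| 40% | 21.7% | 18.0% |
| 60% | 35.5% | 30.0% |

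**3. What the planned summary returns (same model, p = 40%).**
- All subjects: mean 40.0 weeks (first value) or 41.2 (second). The median is 51 weeks on either date, which is the last visit; it is also 51 at p = 20%.
- Failures only: mean 21.9 or 24.9 weeks.

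**4. Closed-form check, without a test schedule.** Let L = 329 days and λ = −ln(1 − p)/L. The mean among failures is 1/λ − L(1 − p)/p. The all-subject mean is p × (that mean) + (1 − p) × 358.
- p = 0.40: 1/λ = 644; 644 − 329 × 0.6/0.4 = 151 days. All subjects: 0.4 × 151 + 0.6 × 358 = 275 days. With completers stopped at day 323 it is 254 days, so the extra 35 days add 0.6 × 35 = 21 days to the mean.
- Failures only, p = 0.60 against p = 0.30: 140 against 155 days. Halving the risk barely moves this mean.

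**5. Does the censoring date matter for Kaplan-Meier?** Same model, p = 40%, week 48:
- Censoring at the last visit or at nominal T48: 37.6% under either event date, equal to the confirmed proportion.
- Censoring each completer at that subject's own last test in T42-45: 41.4% with the first-value date and 100% with the second. Subjects who tested below 200 leave the risk set at that test. With the second-value date, only subjects about to be confirmed remain at T48.

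**6. Secondary check: dropout and the crude VF percentage.** With p the true VF risk, d the dropout risk, h = −ln(1 − p)/48 and g = −ln(1 − d)/48, the crude percentage is h/(h + g) × [1 − exp(−48(h + g))]. The upper bound, counting every leaver as VF, is 1 − (1 − p)(1 − d). At p = 40%:
- d = 6.25%: crude 38.8%, upper bound 44%.
- d = 10%: 38.1% and 46%.
- d = 30%: 34.2% and 58%.

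The 6.25% is 1 of 16 in CD01-Extension before week 48 (protocol 1.4.2.8). It is a weak guide, because those subjects had already passed 12 weeks without VF and the threshold was 400. The other two rates have no source.

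**The case against.** The best defence is that the plan is descriptive and every value is listed by subject (SAP section 8), so either date and a Kaplan-Meier curve can be recovered. The protocol's Kaplan-Meier statement also still stands. That is true, but listings do not say which date the reported figure uses, and a mean of censored times misleads with or without a p-value.

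Several stronger readings are tempting and should not be drawn.

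- **That programmers could report a mean of about 22 or about 41 weeks.** The text favours all subjects. SAP 8.2.2.2 names the ITT and PP populations, 7.5.5 supplies a formula for those without VF, and 8.2.2.4 to 8.2.2.7 say so when a subset is meant. A failures-only mean would also largely repeat SAP 8.1.6.
- **That an isolated earlier value of 200 or more counts as the event.** The formula is headed for subjects with VF and follows the definition of the consecutive pair, so this is over-literal.
- **That censoring after ART restart distorts every estimate.** It inflates the mean. For completers it leaves Kaplan-Meier at weeks 24 and 48 unchanged (step 5). For leavers it depends on whether ART restarted before termination; protocol 5.2.2 makes that possible but not certain.
- **That dropout seriously biases the VF percentage.** This follows only by implication from SAP 6.1, 7.3 and 8.2.2.1, and its size rests on assumed rates. Disposition, ART and completion summaries (SAP 8.1.1, 8.1.5, 8.1.6 and 8.2.2.8) partly expose it.

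**Conclusion.** The point holds. SAP 7.5.5 contradicts itself on the VF date. SAP 8.2.2.2 applies an unsuitable summary to a variable the SAP calls censored, and the protocol's Kaplan-Meier display is missing. A primary efficacy measure cannot be programmed unambiguously from this text and should be corrected before database lock.

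The contradictions need no assumption. Their size does: constant hazard, no extra draws (protocol 4.2 allows them, and they would shorten the gap), and rebound risks of 20% to 60%. On that basis the choice of date moves week-24 VF by about 2 to 5.5 percentage points. The all-subject median can be nothing more than the last visit.

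The 28 to 35 days on ART matter for the mean only. Dropout is a secondary, assumption-based note.

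**What to change.** 1. Use one VF date in the text and formula of SAP 7.5.5 and in 7.5.7, for example the first value of the confirmed consecutive pair.
2. Replace the mean/SD summary in 8.2.2.2 with Kaplan-Meier cumulative VF by group at weeks 24 and 48, with numbers at risk and the median if reached.
3. Censor non-failing completers at one common time, nominal T48, and not at each subject's own last T42-45 test (step 5 shows why). Note that the T48 RNA follows the scheduled ART restart. Censor subjects who restart ART early, change dose without confirmed VF, or withdraw at their last assessment on assigned-dose monotherapy.
4. Optionally, add a sensitivity analysis counting early discontinuation or unscheduled ART restart as failure, labelled as an upper bound because it overstates VF (step 6).
5. Reconcile SAP 7.3 (no imputation) with protocol 8.6.4 (imputation for ITT, to be detailed in the SAP).
6. Correct all six cross-references, each shifted by two: 8.2.2.1 to 7.5.4; 8.2.2.2 to 7.5.5; 8.2.2.4 and 8.2.2.6 to 7.5.6; 8.2.2.5 to 7.5.7; 8.2.2.7 to 7.5.8.
7. Reconcile the rescue note in SAP 3.1.2 and 8.2.2.3, which also covers failure to maintain suppression, with the Part 2 entry passages (for example protocol section 3), which describe entry after VF. Which is intended is for the sponsor to state.

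The cost is SAP wording and a few more standard tables. No new data are needed.
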